1.0 Study Synopsis

Brief Title / Acronym	OPTIMATE
Full Study Title	OPTImization of Medication by transdisciplinary Assessment of drug Treatment in Elderly hospitalized patients: application of a definitive intervention by physicians or clinical pharmacists.
Study Sponsor	University College Cork (UCC)
Abstract (Brief)	
Background: Recurrent hospitalization and unplanned emergency department (ED) attendance resulting from potentially inappropriate medication is an increasingly common phenomenon in older people with multi-morbidity and associated polypharmacy. With a growing older population with multi-morbidity/polypharmacy, there is a pressing need to address the increasing challenge of potentially inappropriate medications (PIMs) and potential prescribing omissions (PPOs) and associated problems that accentuate adverse drug reactions/events and avoidable excess morbidity. There is also an imperative to curb excess healthcare expenditure related to preventable medication-related problems.
 
Objective: To test the clinical and economic impact of a multi-faceted medication optimization definitive intervention (DI) on avoidable rehospitalization and unscheduled ED attendance in multi-morbid patients aged ≥ 70 years hospitalized with acute illness.
 
Design: A randomized controlled clinical trial is proposed in which it is anticipated to randomize 3 x 463 patients to one of 3 groups: (a) standard pharmaceutical care, or (b) trained physician-implemented DI, or (c) clinical pharmacist-implemented DI.
 
Setting: Acute care environment in 3 large tertiary referral teaching hospitals with similar custom and practice relating to management of older people with acute illness.

Participants: Patients aged ≥ 70 years with multi-morbid illness i.e. ≥ 3 chronic medical conditions and associated polypharmacy i.e. ≥ 5 daily prescription medications admitted with acute unselected illness.

Intervention: The definitive multi-faceted intervention will consist of the following components: (i) modified structured history of medication (mSHiM), (ii) Screening Tool of Older Persons' Prescriptions (STOPP) and Screening Tool to Alert to Right Treatment (START) screening for PIMs and PPOs using STOPP/START version 3, (iii) drug-drug interactions screening, using Stockley's Drug Interaction Checker (iv) face-to-face consultation with attending hospital physicians to discuss PIMs, PPOs, interactions and other issues, (v) pre-discharge medication review and adjustment, (vi) detailed medication adjustment discharge report to patients' general practitioners (GPs), (vii) follow-up contact with patients' GPs and community pharmacists at 1 week and 1 and 6 months post-discharge.

Patients in the control arm (standard pharmaceutical care) will receive a sham intervention i.e. modified Medication Adherence Rating Scale (MARS) questionnaire.

Outcome measures: Primary endpoints will include: (i) unscheduled readmission within 30 days post-discharge, (ii) unscheduled readmission within between 90 and 180 days post-discharge, and (iii) ED attendance within 30 days and between 90 and 180 days post-discharge. A primary composite endpoint of unscheduled readmission or ED attendance within 30 days and between 90 and 180 days post-discharge will also be ascertained. Secondary endpoints are: (i) quality of life measured by EQ5D-5L instrument (incorporating pain control) at 30 days and at between 90 and 180 days post-discharge, (ii) all-cause mortality at 30 days and at between 90 and 180 days post-discharge, (iii) first admission to residential care facility for long-term nursing care at 30 days and at between 90 and 180 days post-discharge. Treatment effects for each of the two active intervention arms (versus control) will be estimated and equivalence tests comparing the two active arms (for each outcome) will be undertaken to determine the effectiveness of the DI as delivered by a physician compared to a pharmacist.

An economic evaluation of the DI as delivered by a trained physician and by a trained pharmacist will also be undertaken, involving

- Quality Life Adjusted Year (QALY),
- cost per hospital readmission avoided, and
- cost per ED attendance avoided.

Time frame: 36 months from project start to final report submission.

	
Participating centres: UCC/Cork University Hospital, University Hospital Waterford, University of Ghent/Ghent University Hospital, Health Research Board Clinical Research Facility, Cork (HRB CRF-C).

Study Design	Interventional Randomized Controlled trial.
Study Population	1389 older people presenting to hospital with acute illness for unscheduled admission lasting > 48 hours.
Entry Criteria	
Inclusion Criteria:
 
 a. Age \geq 70years b. 3 or more chronic conditions. c. \geq 5 daily medications pre-admission, all medications taken for at least 4 weeks continuously. d. Can speak and understand English (in the two Irish medical centres), and Dutch or French in Ghent University Hospital (Ghent is predominantly Dutch-speaking). e. Can give written informed consent, or give witnessed verbal consent or have a suitable proxy who is able to give informed assent on the patient's behalf. f. Agrees to follow-up contact post-discharge up to 180 days post-discharge. g. Agrees to primary researcher contacting the GP and community pharmacist post-discharge. 
Exclusion Criteria:
 
 a. Terminal illness. b. Severe dementia and clearly unable to understand the purpose of the trial or give consent to participation. c. Severe communication disorder, making informed consent impossible. d. Likely to be discharged from hospital within 48 hours of arrival. e. Intensive Care Unit (ICU) admission.

	
 f. Primary psychiatric presenting illness. g. Unavailable for post-discharge follow-up for any reason. h. Non-accidental poisoning. i. Previous participation in medication optimization trials. j. Active participation in another clinical trial k. Infectious illness requiring strict isolation (including COVID-19 infection) blocking access of the primary researcher to the patient for enrolment. l. End-stage renal, liver or lung disease requiring organ replacement therapy. m. Admitted under the care of specialists in Clinical Pharmacology, Palliative Medicine, Clinical Oncology or Haematology. n. Admitted under the care of specialists in Geriatric Medicine in Ghent University Hospital. o. Trial participation refusal.
Estimated Study start and End Dates	Start date: 26/09 /2022 End date: 15/07/2024
Data collection and Statistical Analysis.	All OPTIMATE trial data will be collected electronically and entered on a bespoke trial proforma. Once verified as fully correct and complete, all individual participant trial data will be stored on a fully secure clinical trial database, the Castor electronic data capture system (Castor EDC) on the server located in the Netherlands. The Castor EDC system is compliant with ICH E6 GCP, GDPR, ISO 27001 and ISO 9001 standards and regulations. On completion of all OPTIMATE trial data collection, the database will be locked down and trial statistical analysis will commence. The data analysis will be completed no later than 30/11/2024 when a Final Project Report will be submitted to the Health Research Board, the trial funding body.

Dissemination of results	The results of this trial will be presented at national and international conferences and published in relevant journals.
---------------------------------	---

2.0 Background and Significance of the question

2.1 Introduction

Research consistently shows that 5-6% of all acute hospitalizations result from adverse drug reactions (ADRs; Kongkaew et al.). This proportion approximately doubles in older people with multimorbidity and related polypharmacy (i.e. ≥ 5 daily prescription medications; Oscanoa et al.). Polypharmacy which results from multimorbidity predisposes to drug-related problems (DRPs), potentially inappropriate medications (PIMs), potential prescribing omissions (PPOs), medication non-adherence, medication errors and accidental overdose, all of which heighten risk of ADRs ([name]). These medication-related problems can individually or in combination lead to hospitalization, more commonly in older people (Al Hamid et al.; Thomsen et al.). A recent systematic review indicates that approximately two-thirds of hospital readmissions relating to adverse medication in older people are preventable (El Morabet et al.). Previous studies show that older people in transition from hospital to the community experience prescribing errors and problems with medication information transfer more commonly, resulting in various DRPs that are commonly detrimental to patients (Laugaland et al.). Recurrent hospitalizations (including 1-month readmissions affecting at least 21.9%-22.3% of patients (McAuliffe et al.; Ravn-Nielsen et al.) and unplanned emergency department (ED) attendances arising from potentially inappropriate medication are common in multimorbid older people, and costly (Hyttinen et al.; Leendertse et al.), but preventable. Previous studies also show that older people exposed to PIMs and PPOs in the community experience excess hospitalization and ED attendance (Xing et al.; Moriarty et al.). Hence, any definitive intervention for minimizing rehospitalization/ED attendance in multi-morbid older people should include components for minimizing PIMs and PPOs.

A recent multi-centre randomized clinical trial (RCT) called SENATOR ([name] et al., 2020) examined the effect of a software intervention for applying STOPP/START PIM and PPO criteria (version 2; [name] et al., 2015) along with potentially adverse drug-drug and drug-disease interaction identification in hospitalized multi-morbid older patients on incident ADRs within 14 days of randomization. The trial which eventually randomized 1537 patients showed no difference in ADR incidence between intervention patients (24.5%) and control patients receiving standard pharmaceutical care (24.8%). Importantly, the overall implementation rate of software-generated medication recommendations by attending clinicians in their patients' medication lists was only 15% in the intervention arm. A previous single centre clinical trial had shown that delivery of STOPP/START recommendations in person by a trained physician resulted in 81.2% implementation of STOPP recommendations and 87.4% implementation of START recommendations (O'Connor et al.); the number needed to treat (NNT) to prevent one non-trivial incident ADR in that trial was eleven. A parallel study of STOPP/START recommendations (as part of a multi-faceted, software-supported medication optimizing intervention) being delivered in person by a clinical pharmacist resulted in STOPP recommendations being applied in 39.2% and START recommendations in 29.5% of cases

OPTIMATE Trial

Principal Investigator: [name] [name]

([name] et al.). This disparity has raised important questions about the impact of pharmacists in optimizing hospitalized older multi-morbid patients' medications (Dalton et al.).

More recently, a Danish RCT (OPTIMIST trial) examined the effect of a multi-faceted clinical pharmacist-delivered intervention (basic and extended) based on medication review during hospitalization compared with standard pharmaceutical care (Ravn-Nielsen et al.). The trial concluded that applying the extended clinical pharmacist intervention which included a motivational interview with patients and post-discharge follow-up with the patients' GPs and community pharmacists significantly reduced all-cause readmission within 30 days (hazard ratio [HR] of 0.62, 95% CI 0.46-0.84) and within 180 days (HR 0.75, 95% CI 0.62-0.90) and the proportion of patients experiencing the primary composite endpoint of readmission or emergency department attendance within 180 days (HR 0.77, 95% CI 0.64-0.93) compared to matched patients receiving standard pharmaceutical care. The NNT to prevent the composite primary endpoint with the extended pharmacist intervention was 12. The cost-benefit ratio of the extended pharmacist intervention is, however, unknown. The OPTIMIST trial included adult patients over 18 and randomized a total of 1498 patients. Importantly, less than 50% of randomized patients were aged over 65. In the over-65 age group, the impact of the extended pharmacist intervention was statistically significant whilst its impact in the under-65s was not significant. Furthermore, the extended intervention showed a significant effect on the primary composite endpoint in patients of all ages taking > 8 daily drugs at admission but was not significant in patients taking ≤ 8 daily drugs. That is, the extended pharmacist intervention was particularly effective in patients over 65 taking > 8 daily medications.

A cost-benefit analysis of the physician-delivered STOPP/START intervention RCT of O'Connor et al. indicates that it was not cost-effective (O'Brien et al.); in contrast, the pharmacist-delivered intervention in the parallel RCT by [name] et al. was found to be cost-effective. However, this analysis focused only on in-hospital ADR prevention. The OPTIMATE study proposes to measure cost effectiveness of the DI from the wider public health services perspective, principally the possible benefits derived from avoidance of unscheduled rehospitalization and emergency department attendance. The cost effectiveness analysis will focus on these events, as they are the costliest consequences in financial terms of adverse medication in older multimorbid patients. Quality of life improvement arising from medication optimization interventions is an important theoretical but so far unproven potential benefit for multimorbid older people. This aspect of the DI in OPTIMATE will also be assessed by measurement of quality of life in all randomized patients during post-discharge follow-up period.

From the OPTIMIST trial findings, it is likely that a definitive intervention (DI) most likely to succeed in optimizing medication in hospitalized multi-morbid older people with polypharmacy will be multi-faceted and sustained both during and after the index hospitalization. Furthermore, the DI should incorporate detailed discussion of proposed medication adjustments with the patient, the attending hospital physician, the GP and the community pharmacist in order to maximize its implementation and impact. Additionally, based on well-established published evidence, the DI should be focused on medication optimization at all points of care transition in older people, especially hospital discharge when the risk of inappropriate medication exposure is highest (Cardwell; Weir et al.).

Given the positive results of the OPTIMIST trial arising from an extended pharmacist intervention designed to optimize medication and the positive results of the RCT by O'Connor et al., direct comparison of physician versus pharmacist delivery of the DI is logical. Furthermore, direct comparison between physician- and pharmacist-delivered DI is important since the particular healthcare professional training of the person performing the DI would have an important bearing on

the roll-out of the DI into routine clinical practice, if shown to have significant benefit for multi-morbid older people compared to usual pharmaceutical care. It is also logical to use easily measurable endpoints that are both clinically and economically important as well as being comparable to similar trials in multimorbid older people exposed to polypharmacy.

In summary, a recent multi-centre trial (OPTIMIST) showed important positive effects of the structured pharmacist intervention on post-discharge readmission/ED attendance among older patients with polypharmacy. The previous single-centre trials in Cork also showed the positive impact of physician-delivered and pharmacist-delivered medication advice interventions, both based on STOPP/START criteria. The larger-scale, international, multi-centre SENATOR and OPERAM trials based on computerized STOPP/START interventions did not show a positive impact on incident ADRs within 14 days (SENATOR) or drug-related hospitalizations within 12 months (OPERAM, Blum et al.) largely resulting from suboptimal adherence with medication advice among attending physician prescribers.

2.2 Aims of the study

- (i) Primary aim: to determine if a medication optimization DI can significantly reduce all-cause re-hospitalization and unscheduled emergency department attendance at 30 days and between 90 and 180 days in multi-morbid older people exposed to polypharmacy. To achieve this, we will measure the following outcomes: Unscheduled readmission within 30 days and between 90 and 180 days post-discharge, ED attendance within 30 and between 90 and 180 days post-discharge, and a primary composite endpoint of unscheduled readmission or ED attendance within 30 and between 90 and 180 days post-discharge.
- (ii) Secondary aims:
 - (a) To determine the effects of the DI on secondary endpoints, including quality of life (EQ5D-5L), all-cause mortality and referral to nursing home for long-term care.
 - (b) To compare endpoints achieved through standard pharmaceutical care (control) with those achieved through physician-delivered DI and pharmacist-delivered DI. This is to determine if DI delivery by a trained pharmacist is more/less/equally effective compared to DI delivery by a trained physician.

2.3 Research Question /Hypothesis

Hypothesis 1: A multi-faceted medication optimization definitive intervention (DI) based on explicit inappropriate prescribing criteria, potential prescribing omission criteria and drug-drug and drug-disease interaction surveillance applied following admission and pre-discharge from hospital in older people with multi-morbid illness and associate polypharmacy supplemented by structured follow-up with patients' GPs and community pharmacists as well with patients themselves results in significantly lower rates of unscheduled rehospitalization or emergency department attendance or both compared to standard current pharmaceutical care.

Hypothesis 2: The same multi-faceted medication optimization DI has an equal effect on rates of unscheduled rehospitalization or emergency department attendance or both when delivered by a trained pharmacist compared to a trained physician.

3.0 Trial Objectives and Purpose

3.1 Primary objective(s)

- To test by RCT the effects of the definitive prescribing optimization intervention delivered to attending hospital physician/prescribers on unscheduled rehospitalization or emergency department attendance or both compared to standard current pharmaceutical care.
- To compare by RCT the effects of the definitive prescribing optimization intervention delivered by trained physicians, with the effects of the definitive prescribing optimization intervention delivered by trained clinical pharmacists on unscheduled rehospitalization or emergency department attendance or both.
- To complete the RCT (including all patient follow-ups) within 24 months.
- To deliver an RCT results report within 6 months of completion of patient follow-up.
- To publish the RCT findings in a high impact biomedical journal within 6 months of completion of all trial data analysis.

3.2 Secondary objective(s) (if applicable)

- To examine the effectiveness of the definitive intervention on quality of life as measured by EQ5D-5L.
- To examine the effectiveness of the definitive intervention on all-cause mortality.
- To examine the effectiveness of the definitive intervention on nursing home disposition.
- To examine the cost-effectiveness of the definitive intervention as measured by Quality Life Adjusted Year (QALY), cost per hospital readmission avoided and cost per ED attendance avoided.

3.3 Safety Objectives (if applicable)

- To minimize the prevalence of medications to be avoided in multimorbid older people.

4.0 Description of methodology

4.1 Type of Study- study design

OPTIMATE is designed as a prospective, single-blinded, randomized controlled multi-centre study.

4.2 Recruitment of study participants

OPTIMATE will focus on patients admitted with acute medical or surgical illness admitted to Cork University Hospital, University Hospital Waterford and Ghent University Hospital. The OPTIMATE trial will be multi-centre, involving individual level patient randomization. The 3 participating centres are large university medical centres of comparable size, diversity of medical and surgical specialties and acute admission and discharge procedures. This is to ensure that the proposed trial can recruit appropriate patients who meet the inclusion criteria efficiently so that the trial can be completed within the proposed time frame.

4.2.1 Subjects Eligibility Criteria

Inclusion criteria:

- I. Age \geq 70 years (male or female).
- II. \geq 3 chronic medical conditions.
- III. \geq 5 daily medications pre-admission, all medications taken for at least 4 weeks continuously.
- IV. Can speak and understand English (in the two Irish medical centres), and Dutch or French in Ghent University Hospital (Ghent is predominantly Dutch-speaking).
- V. Can give written informed consent, or give witnessed verbal consent or have a suitable proxy who can give informed assent on the patient's behalf.
- VI. Agrees to follow-up contact post-discharge up to 180 days post-discharge.
- VII. Agrees to primary researcher contacting the GP and community pharmacist post-discharge.

Exclusion criteria

- I. Terminal illness.
- II. Severe dementia and clearly unable to understand the purpose of the trial or give consent to participation.
- III. Severe communication disorder, making informed consent impossible.
- IV. Likely to be discharged from hospital within 48 hours of arrival.
- V. ICU admission.
- VI. Primary psychiatric presenting illness.
- VII. Unavailable for post-discharge follow-up for any reason.
- VIII. Non-accidental poisoning.
- IX. Previous participation in medication optimization trials.
- X. Participation in another clinical trial.
- XI. Infectious illness requiring strict isolation (including COVID-19 infection) blocking access of the primary researcher to the patient for enrolment.
- XII. End-stage renal, liver or lung disease requiring organ replacement therapy.
- XIII. Admitted under the care of specialists in Clinical Pharmacology, Palliative Medicine, Clinical Oncology or Haematology.
- XIV. Admitted under the care of specialists in Geriatric Medicine in Ghent University Hospital.
- XV. Trial participation refusal.

4.3 Sampling and Randomization (if applicable)

To test the main study hypothesis i.e. that the definitive intervention (DI) yields significantly better outcomes than standard pharmaceutical care (control), patients will be randomized in a 1:1:1 ratio to one of 3 trial arms: (a) standard pharmaceutical care as it contemporaneously exists in that hospital, or (b) trained physician-delivered intervention or (c) clinical pharmacist-delivered intervention. The 3-way randomization to control, Physician-DI and Pharmacist DI is fundamental to addressing the important secondary question: does physician-delivered DI offer any advantage over pharmacist-delivered DI?

The sample size is based on a known 180-day risk of medication-related readmission of approximately 20%. At a bilateral 5% significance threshold and 80% power, for detection of an 8% absolute reduction in readmissions, with a 1:1:1 randomization, each group must contain 324 patients i.e. 972 patients in total. With the expectation of up to 30% patient attrition, we aim to randomize $972/(1-0.3) = 1389$ patients.

The randomization will be designed by the trial statistician, but the code to create the resulting randomization lists will be executed by an independent statistician. The resulting lists will be integrated into the electronic data capture system in a manner such that trial staff never have access to the lists. Allocation of enrolled patients into treatment arms will then be delivered using a web-based system, such that the allocation remains concealed until a patient is unambiguously consented and enrolled onto the trial and cannot be altered in the underlying database once it is revealed. While the intervention will be known to clinical staff, the trial statistician and outcome assessors will remain blinded until the results are finalized.

Within 72 hours of admission, patients who are potentially suitable for trial enrolment will be approached by the primary researchers (PRs) and informed about OPTIMATE in outline. If they meet inclusion criteria and do not have exclusion criteria, they will be asked to provide informed consent to trial enrolment. Recommended best practice for assessment of decision-making capacity of older patients who may be suitable for the OPTIMATE trial, involves formal assessment of capacity. Where necessary, the patient's mental capacity will be evaluated using the **OPTIMATE Decision-Making Capacity Functional Assessment** guidelines document in the OPTIMATE Manual of Operations. The patient will then be randomized to either the control arm (usual pharmaceutical care), pharmacist-delivered DI arm or physician-delivered DI arm of the trial. Randomization will proceed in a 1:1:1 ratio. The randomization process will be performed electronically using Castor EDC's block randomization algorithm. Patient enrolment will be sequential. With individual level randomization, there is the theoretical risk of control group contamination. This is where both control and intervention patients could be under the care of the same physician, thereby presenting a risk of medication advice learnings in intervention patients being applied unwittingly to control patients. However, in practice, as was seen in the pre-SENATOR observation study (Lavan et al.), variation in reported incidence of ADRs across various medical and surgical specialties in the 6 multi-national participating clinical sites was so large that meaningful cluster randomization was considered both impractical and unnecessary. Furthermore, in the SENATOR trial itself ([name] et al.), although uptake of medication optimization advice was generally poor, there was no evidence of contamination of the control population.

Randomization will be stratified by study site and by admitting service type (i.e. medical vs. surgical). The stratum-specific randomization lists will be generated electronically within Castor EDC, using a validated variable block randomization model. Once a patient has given consent and been enrolled onto the study, their data will be irreversibly added to the study database. From this point, the

primary researchers will receive randomization outcomes immediately upon activating the randomization request on the electronic Case Report Form (eCRF) within the Castor EDC.

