4.0 Study Procedures and Schedule of Events

The schedule of trial procedures for patient participants in the intervention arm of the trial are shown in Tables 1a and 1b below. To mimic the intervention for blinding purposes of the participants, both control and intervention arm patients will receive a sham intervention in the form of a modified version of the Medication Adherence Rating Scale (MARS; Thompson et al.).

Table 1a: Schedule of events for intervention patients

Timepoints	0/1	2	3	4	5
Study Visit	Baseline (within 72 hours of admission)	Pre-discharge (within 48 hours pre-discharge)	1 Week Follow-up (within 10 days post-discharge)	1 Month Follow-up (within 30 days post-discharge)	6 Month Follow-up (between 90 and 180 days post-discharge)
	Day 1	Day variable	Day 10 (+/- 3 days post-discharge)	Day 30 (+/- 7 days post-discharge)	Between Day 90 and Day 180 post-discharge
Inclusion / Exclusion criteria	X				
Decision-Making Capacity Functional Assessment	X	X**		X**	X**
Informed consent/ proxy assent	X	X**		X**	X**
Patient Demographics	X				
Medical History	X	X		X	X
Medication Reconciliation	X	X		X	X

OPTIMATE Trial

Principal Investigator: [name] [name]

FORTA* criteria	X	X		X	X
Laboratory Results	X	X			
Electrocardiogram review	X				
EQ5D-5L				X	X
Randomization	X				
Medication History (modified SHiM)	X				
Modified Medication Adherence Rating Scale (mMARS)	X				
Barthel Index Score	X	X			
Drug-drug interactions (Stockley's)	X	X		X	X
STOPP/START criteria (PIMs & PPOs*)	X	X		X	X
Face-to-face discussion with senior attending physician or senior resident to highlight potentially inappropriate PIMs and PPOs	X	X			
Face-to-face discussion with patient or nominated proxy (where patient does not have decision-making capacity) to explain details of recommended medication changes.		X			

OPTIMATE Trial

Principal Investigator: [name] [name]

Pre-discharge medication review, documentation of agreed medication adjustments and preparation of report for patient's GP with detailed explanation of recommended medication changes.		X			
Telephone contact with patient's GP to discuss medication changes.			X		
Telephone contact with patient or nominated proxy (where patient does not have decision-making capacity) to define current list of medications, discuss any medication issues and ascertain endpoint information.				X	X
Telephone contact with patient's pharmacist to define medication currently dispensed.			X	X (if necessary)	X (if necessary)

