6.0 Outcome measures

6.1 Primary Outcome

- (i) unscheduled readmission within 30 days post-discharge,
- (ii) unscheduled readmission between 90 and 180 days post-discharge, and
- (iii) ED attendance within 30 and between 90 and 180 days post-discharge.

A primary composite endpoint of unscheduled readmission or ED attendance within 30 and between 90 and 180 days post-discharge will also be ascertained.

Treatment effects for each of the two intervention arms versus the control arm will be estimated for each outcome. Equivalence tests comparing the two active arms (for each outcome) will be done to compare DI delivery by physician with DI delivery by pharmacist.

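### The only power statement rests on medication-related readmission, but the primary endpoints carry no such restriction, so 80% power is not shown for any of them

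*Combined protocol and SAP*

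**What the plan says.** Section 4.3 holds the only sample-size statement. "The sample size is based on a known 180-day risk of medication-related readmission of approximately 20" percent, with a two-sided 5% level and 80% power, "for detection of an 8% absolute reduction in readmissions", gives 324 per group and 972 in all. "With the expectation of up to 30% patient attrition" then raises the number to randomise to 1389, or 463 per arm.

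The endpoints are described differently elsewhere:

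- Section 2.2 (primary aim) asks whether the intervention "can significantly reduce all-cause re-hospitalization and unscheduled emergency department attendance at 30 days and between 90 and 180 days".
- Section 2.3 (hypothesis 1) speaks of "significantly lower rates of unscheduled rehospitalization or emergency department attendance or both compared to standard current pharmaceutical care".
- Section 6.1 lists readmission and ED attendance as primary outcomes, and adds: "A primary composite endpoint of unscheduled readmission or ED attendance within 30 and between 90 and 180 days post-discharge will also be ascertained". No outcome there is limited to drug-related events.
- Tables 1a and 1b in the schedule of events record only whether an unscheduled readmission or ED attendance took place.
- Section 7.2 models readmission as a binary outcome by logistic regression, each active arm against control.

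The synopsis objective is the nearest to a restriction by cause, with "avoidable rehospitalization and unscheduled ED attendance in multi-morbid patients". That adjective is not carried into any endpoint definition.

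**The concern.** A power figure describes one event, one time horizon and one target difference. Here the control risk is that of medication-related readmission by 180 days, while the trial collects and tests readmission and ED attendance without regard to drug cause. The risk of the wider event cannot be read off the risk of the narrower one. An 8-point fall from 20% is also a 40% relative reduction (8/20), and the plan does not say which of the two scales would carry over to a wider event.

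The interpretation of the result is at stake. Section 7.2 reports every outcome without multiplicity correction and leaves the weighing to readers, who need to know what difference the trial could detect. A null result on a primary endpoint could be read as coming from an 80%-powered comparison, although the plan does not show that.

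**Working it through.** **Inputs.** From section 4.3: control risk 20%, reduction 8 points (so 12% on treatment), two-sided 5%, 80% power, 324 evaluable per arm, attrition up to 30%. From section 2.1: 1-month readmission of at least 21.9% to 22.3%, from cited studies. The control risks of 15%, 22% and 30% used below are assumptions, because the plan gives none for a primary endpoint. The 22% lies close to the section 2.1 figure; 15% and 30% bracket the planned 20%.

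**The plan's own figure.** With p1 = 0.20, p2 = 0.12, mean m = 0.16 and d = 0.08:

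- Unpooled: n = (1.960 + 0.842)² × (0.1600 + 0.1056) / 0.08² = 325.7, so 326 per arm.
- Pooled variance: n = [1.960 × √(2 × 0.16 × 0.84) + 0.842 × √0.2656]² / 0.08², so 329 per arm.
- Arcsine: 324.9, so 325 per arm.
- Attrition: 972 / (1 − 0.30) = 1389.

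The stated 324 agrees with all three to within 2%. Power at 324, pooled z test:

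power = Φ{ [d√n − 1.960√(2m(1−m))] / √(p1(1−p1) + p2(1−p2)) } = Φ{ (1.440 − 1.016) / 0.515 } = Φ(0.822) = 79.5%.

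The calculation is sound for the inputs it names.

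**Matching the inputs to the endpoints.**

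| Element | Section 4.3 | Primary endpoints (section 6.1) |
|---|---|---|
| Cause | medication-related for the control risk; unqualified for the effect | no restriction; all-cause in section 2.2 |
| Event | readmission | readmission, ED attendance, either of them |
| Horizon | 180 days | within 30 days; between 90 and 180 days |
| Control risk | 20% | none given |

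The 180-day horizon does not serve the 30-day endpoints. Whether it fits the later endpoints depends on how the 90 to 180 day interval is to be read. The schedule also uses that interval as a visit label, "6 Month Follow-up (between 90 and 180 days post-discharge". That is a separate question of endpoint definition and is not needed for this point.

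**What power would be under other control risks.** Same formula, two-sided 5%. For example, 22% to 14% at 324 per arm: (1.440 − 1.065) / 0.540 = 0.694, so 76%. And 30% to 18%: (2.160 − 1.184) / 0.598 = 1.632, so 95%.

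| Control risk | 8 points, 324 per arm | 40% relative, 324 per arm | 8 points, 463 per arm | 40% relative, 463 per arm |
|---|---|---|---|---|
| 15% (assumed) | 90% | 65% | 97% | 80% |
| 20% (section 4.3) | 79% | 79% | 91% | 91% |
| 22% (assumed) | 76% | 84% | 89% | 94% |
| 30% (assumed) | 64% | 95% | 79% | 99% |

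The 463 columns show no attrition and the 324 columns the full 30%. As the control risk rises, power falls if the absolute effect is held and rises if the relative effect is held. The plan fixes neither the risk nor the scale for a primary endpoint.

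**The case against.** The best defence is that one adjective has strayed into one sentence. Section 4.3 states the effect as a reduction in readmissions without qualification, and it says it is testing the main hypothesis, which is not limited to drug-related events. If 20% was meant as the 180-day risk of any unscheduled readmission, what remains is a wording slip and an unsourced figure. This stands as a real possibility. It rules out the firmer reading, which some would draw, that the 80% certainly belongs to no analysed endpoint. It does not supply the missing support: even then the 80% would cover 180-day readmission only, and not 30-day readmission, ED attendance or the composite.

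A reader might also infer that an all-cause 20% at 180 days is impossible, because section 2.1 cites more than that at one month. The documents do not support this. Those figures come from other populations, and the sentence can be read as tying them to inappropriate medication.

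The Danish pharmacist trial in section 2.1 offers a possible anchor. Its number needed to treat of 12 for readmission or ED attendance is about 8.3 points (1/12), close to the planned 8. But section 4.3 does not cite it, and it does not give a control risk. If that trial's hazard ratio of 0.77 is converted under proportional hazards, differences of 7.5 and 8.6 points correspond to control risks of 40% and 50%, not 20%.

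Finally, section 7.2 promises 95% confidence intervals for every outcome, so a null result can be judged by its interval. That limits the harm of an unclear power claim, but it does not make the claim correct.

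**Conclusion.** The mismatch is real and should be corrected. As written, 80% power is not shown for any primary endpoint, and no control risk, target effect or power is given for ED attendance or the composite. The sample-size arithmetic is not at fault.

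A reader might conclude that the trial is underpowered. The documents do not show that, nor the opposite. At 324 per arm, power runs from 64% to 95% over the assumed control risks and the two effect scales, and the direction changes with the scale. These figures rest on the assumed risks, a simple two-group comparison without covariate adjustment, and attrition at its stated ceiling. They illustrate how far the answer can move and do not estimate the trial's power. The mismatch of wording is certain; whether it reflects a wrong planning input or a slip cannot be settled from the documents.

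**What to change.** Amend section 4.3, and carry the same text into the SAP that section 7.2 says will be registered before database lock. Keep the 20% to 12% derivation visible, since it explains the 324, and state which event the 20% describes and its source. Then:

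- **If it is medication-related readmission:** say that the 80% does not apply to the analysed primary endpoints. Add the power or detectable difference at 324 evaluable per arm for one named primary endpoint and window, over a short range of control risks that includes values below and above 20%, and say whether the effect is absolute or relative.
- **If it was meant as unscheduled readmission from any cause:** delete the qualifier, give the source, and say that the 80% covers 180-day readmission only and not 30-day readmission, ED attendance or the composite.

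The cost is a few sentences. Sample size, data collection and analysis stay as they are. The drawback is that the stated power may become less favourable.
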